10.4.5 Analysis of Exploratory Endpoints

Not applicable.

10.4.6 Statistical/Analytical Issues

10.4.6.1 *Adjustments for Covariates*

No adjustment for covariates is planned for the primary, and **CCI** effectiveness analyses.

10.4.6.2 *Handling of Dropouts*

Available data for subjects that drop out will be used up until the time of dropout. Missing values for the primary endpoint will be imputed as described in Section 10.4.6.3.

10.4.6.3 *Handling of Missing Data*

The primary analysis is based on the FAS that includes only subjects that have received treatment in both hands, so the number of missing values for the primary endpoint is expected to be very low. However, any case of missing a primary endpoint value will be imputed by a within-subject difference of 0 mm. This corresponds to assuming no pain relief using Restylane Skinboosters Vital Lidocaine compared to Restylane Vital and is considered as a worst-case approach.

All other endpoints will be analyzed on available data, i.e., no imputations will be done.

10.4.6.4 *Interim Analyses and Data Monitoring*

Not applicable.

10.4.6.5 *Multicenter Study*

The primary endpoint will be presented descriptively for each of the study sites, including CIs. No other by-site subgroup analysis is planned for this study.

10.4.6.6 *Multiple Comparison/Multiplicity*

As there is only one primary endpoint defined for this study, no adjustment for multiplicity is needed for the primary analysis. For the **CCI** no adjustments for multiplicity will be done. P-values obtained for any endpoint other than the primary will be considered descriptive and only provided for ease of interpretation.

10.4.6.7 *Active-Control Studies Intended to Show Equivalence*

Not applicable.

 EST. 1981	Title 43CH2305 Statistical Analysis Plan	Doc id MA-59378
---	--	---------------------------

Study Number 43CH2305
Statistical Analysis Plan

CONFIDENTIAL

Page 30 of 36
Final, 1.0, date 24APR2024

10.4.6.8 *Examination of Subgroups*

No subgroup analyses are planned for this study except for the study site subgroup analysis of the primary endpoint.

10.4.6.9 *Analysis Visits Definition*

Not applicable. All analyses will be performed using nominal visits.

10.5 Subject Reported Outcomes Analysis

Not applicable.

10.6 Safety Analysis

10.6.1 Adverse Events

All AEs will be coded according to MedDRA and summarized by System Organ Class (SOC), Preferred Term (PT), including number of subjects with at least one event (n, %) and number of events.

For subject counts, a subject will only be counted once per SOC and once per PT in cases where multiple events are reported for a subject within SOC or PT. For event counts, subjects with multiple events in a category will be counted for each event.

The number of subjects with AEs related to study product or study product injection procedure, as well as unrelated AEs, will be presented by SOC, PT, and maximum intensity also including the number of events. Action taken for related AEs will be summarized by SOC and PT using number of events. Serious AEs will be listed.

For AEs related to study product or study product injection procedure, the number of days to onset and the duration of event will be summarized by SOC and PT using mean, standard deviation, median, minimum, and maximum.

In addition, a summary of all AEs will be provided, which will include (but is not limited to):

- frequency of subjects (n, %) with at least one AE and number of events (in total as well as serious AEs),
- frequency of subjects (n, %) with at least one related AE and number of events (in total as well as serious AEs),
- frequency of subjects (n, %) with at least one related AE in the hand treated with Restylane Skinboosters Vital Lidocaine, and number of events (in total as well as serious AEs),
- frequency of subjects (n, %) with at least one related AE in the hand treated with Restylane Vital, and number of events (in total as well as serious AEs),
- frequency of subjects (n, %) with at least one unrelated AE and number of events (in total as well as serious AEs),
- number of subjects who did not have an AE.

GALDERMA <small>EST. 1981</small>	Title 43CH2305 Statistical Analysis Plan	Doc id MA-59378
---	---	----------------------------------

Study Number 43CH2305
Statistical Analysis Plan

CONFIDENTIAL

Page 31 of 36
Final, 1.0, date 24APR2024

CCII

Page 10

CCI [REDACTED]

11 SHELLS OF TABLES, FIGURES AND LISTINGS AND REPORTING OUTPUT (GENERAL FEATURES)

[figure not shown]
A Statistical Analysis Report shell will be produced including all planned TFL shells.

12 APPENDICES

12.1 Visual Analogue Scale (VAS)

Please mark, with a vertical line, how much pain you feel at the different timepoints.

VAS pain assessment RIGHT hand:

VAS pain assessment LEFT hand

Effective date: 2024-04-25 10:28

Effective date:

Effective

Version: 1.0

Study Number 43CH2305
Statistical Analysis Plan**CONFIDENTIAL****Page 32 of 36**
Final, 1.0, date 24APR2024

CCI

[figure not shown]
 EST. 1981	Title 43CH2305 Statistical Analysis Plan	Doc id MA-59378
---	--	---------------------------

Study Number 43CH2305
Statistical Analysis Plan

CONFIDENTIAL

Page 33 of 36
Final, 1.0, date 24APR2024

CCI

12.3 Potentially Clinically Significant Values

Not applicable.

12.4 Model Checking and Diagnostic for Analyses

The histogram of the distribution of the primary endpoint Δ_{T0} , obtained from the t-test procedure as described in Section 12.5 below, will be used to check the normality assumption of the t-test.

12.5 Details of the SAS Code for Analysis

The primary and **CCI** endpoints are to be analyzed using one-sample t-tests, or if deemed necessary, Wilcoxon signed-rank tests.

The analysis will be performed at T0, T10, T20, and T30.

The SAS (from the 9.4 version) syntax that will be used to obtain the one-sided p-values of the t-tests is:

```
proc ttest data=<dataset> h0=0 plots(showh0) sides=1 alpha=0.025;
  var <math>\Delta_T</math> variable;
  ods output Ttests=work.Ttests;
run;
```

The SAS (from the 9.4 version) syntax that will be used to obtain the two-sided confidence intervals around the Δ_T estimates is:

```
proc ttest data=<dataset> h0=0 plots(showh0) sides=2 alpha=0.05;
  var <math>\Delta_T</math> variable;
  ods output ConfLimits=work.ConfLimits;
run;
```

	Title 43CH2305 Statistical Analysis Plan	Doc id MA-59378
--	--	---------------------------

Study Number 43CH2305
Statistical Analysis Plan

CONFIDENTIAL

Page 34 of 36
Final, 1.0, date 24APR2024

The SAS (from the 9.4 version) syntax that will be used to obtain the p-values of the Wilcoxon signed-rank tests (in case needed) is:

```
proc univariate data=<dataset> mu0=0;
  var <math>\Delta_T</math> variable >;
  ods output TestsForLocation=
    work.TestsForLocation(where=(Test='Signed Rank'));
run;
```

Note: the univariate procedure only gives two-sided p-values. Thus, the one-sided p-values for the Wilcoxon tests need to be calculated from the obtained two-sided p-values according to the following:

- If the Δ_T estimate is < 0 then the one-sided p-value is calculated as:
 - (two-sided p-value)/2.
- If the Δ_T estimate is ≥ 0 then the one-sided p-value is calculated as:
 - 1-(two-sided p-value)/2.

The SAS (from the 9.4 version) code that will be used to obtain the two-sided confidence intervals around the Δ_T medians (in case Wilcoxon test is used) by using Bootstrapping is:

```
* Define useful macros */
%macro ODSOff(); /* Call prior to BY-group processing */
ods graphics off; ods exclude all; ods noresults;
%mend;

%macro ODSOn(); /* Call after BY-group processing */
ods graphics on; ods exclude none; ods results;
%mend;

proc surveyselect data=<dataset> out=BootSamples noprint seed=59378
  method=urs
  OUTHITS
  samprate=1 reps=10000;

run;

%ODSOff /* suppress output */

proc means data=BootSamples median;
  by Replicate;
  var <math>\Delta_T</math> variable;
  ods output summary=work.summary;
run;

%ODSOn /* enable output */

proc univariate data=summary;
  var <math>\Delta_T</math> variable_median;
  output out=BootStats pctlpts =2.5 97.5 pctlname=P025 P975
```

GALDERMA EST. 1981	Title 43CH2305 Statistical Analysis Plan	Doc id MA-59378
------------------------------	---	----------------------------------

Study Number 43CH2305
Statistical Analysis Plan

CONFIDENTIAL

Page 35 of 36
Final, 1.0, date 24APR2024

```
pctlpre =Median_;  
run;
```

2024-04-25 10:28

Effective date:

Effective

Version: 1.0

GALDERMA EST. 1981	Title 43CH2305 Statistical Analysis Plan	Doc id MA-59378
------------------------------	---	----------------------------------

Study Number 43CH2305
Statistical Analysis Plan

CONFIDENTIAL

Page 36 of 36
Final, 1.0, date 24APR2024

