10.4.1 Effectiveness Data Summary

10.4.1.1 *VAS*

VAS scores will be summarized at each timepoint (T0, T10, T20, and T30) using descriptive statistics (n, mean, standard deviation, median, min and max) by study product based on the FAS.

 EST. 1981	Title 43CH2305 Statistical Analysis Plan	Doc id MA-59378
---	--	---------------------------

Study Number 43CH2305
Statistical Analysis Plan

CONFIDENTIAL

Page 27 of 36
Final, 1.0, date 24APR2024

The within-subject differences (Δ_{T0} , Δ_{T10} , Δ_{T20} , and Δ_{T30}) will be summarized at each post-treatment timepoint using descriptive statistics (n, mean, standard deviation, median, min and max) in the total group based on the FAS.

Frequencies and proportions (n, %) of subjects that have a within-subject difference of less than 0 mm on the VAS will be summarized at each post-treatment timepoint (T0, T10, T20, and T30) in the total group in the FAS.

Summaries will be presented overall.

CCI

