10.4.2 Analysis of Primary Endpoint

The primary endpoint in this study is defined as the within-subject difference in VAS score (Restylane Skinboosters Vital Lidocaine - Restylane Vital) at the end of injection. The null hypothesis that the within-subject difference in VAS score is greater than or equal to 0 mm will be tested against the alternative hypothesis that the within-subject difference in VAS score is less than 0 mm using a one-sample t-test. See Section 3.3.1 for a more formal description of the statistical hypotheses to be tested.

If the one-sided p-value of the test is <0.025 the pain at the end of injection will be considered statistically significantly lower after treatment with Restylane Skinboosters Vital Lidocaine than after treatment with Restylane Vital, and thus the primary objective will be considered met. Results will include mean VAS score by treatment, mean within-subject difference in VAS, and the p-value along with standard descriptive statistics and the two-sided 95% CI around the difference (based on the t distribution).

The results for the primary endpoint will also be presented by study site, descriptively only.

See Section 10.4.6.3 for handling of missing values.

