10.4.3 Sensitivity Analysis of Primary Endpoints

To investigate the assumptions underlying the model, analysis of the distribution of the within-subject differences will be done. If the distribution of the differences seems to be deviating from normal, a Wilcoxon signed-rank test will be used as a sensitivity analysis. However, the statistical hypotheses to be tested will change from the one specified in Section 3.3.1 to the following:

 EST. 1981	Title 43CH2305 Statistical Analysis Plan	Doc id MA-59378
---	--	---------------------------

Study Number 43CH2305
Statistical Analysis Plan

CONFIDENTIAL

Page 28 of 36
Final, 1.0, date 24APR2024

$$\begin{cases} H_0: \tilde{\Delta} \geq 0 \text{ mm} \\ H_1: \tilde{\Delta} < 0 \text{ mm,} \end{cases}$$

[figure not shown]
where $\tilde{\Delta}$ denotes the median within-subject difference in VAS score (Restylane Skinboosters Vital Lidocaine - Restylane Vital) at the end of injection.

To assess the robustness of the primary effectiveness results, the following sensitivity analyses will be conducted:

1. Observed Case (OC) analysis of the within-subject difference in VAS score at T0 on the FAS under Missing Completely at Random assumption,
2. Analysis of the within-subject difference in VAS score at T0 will be repeated on the PPS.

The analyses in 1) and 2) will follow the outline in Section 10.4.2, however, no analyses by study site will be done. If the normality assumption is found to be questionable, 1) and 2) will also be performed using the Wilcoxon signed-rank test.

CCI

	Title 43CH2305 Statistical Analysis Plan	Doc id MA-59378
--	--	---------------------------

Study Number 43CH2305
Statistical Analysis Plan

CONFIDENTIAL

Page 29 of 36
Final, 1.0, date 24APR2024

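### SAP 12.5 chooses the tail of the one-sided Wilcoxon p-value by an undefined estimate; if that is the sample median, a median of exactly 0 gives the wrong tail

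*SAP*

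**What the plan says.** SAP 10.4.3 provides that, if the within-subject differences look non-normal, "a Wilcoxon signed-rank test will be used as a sensitivity analysis". It restates the hypotheses for that test with a parameter that "denotes the median within-subject difference in VAS score (Restylane Skinboosters Vital Lidocaine - Restylane Vital) at the end of injection". Under SAP 12.4 normality is judged from a histogram.

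SAP 12.5 gives the code. It notes that PROC UNIVARIATE returns only two-sided p-values and sets a conversion rule: halve p if the Δ_T estimate is below 0; if the "estimate is ≥ 0 then the one-sided p-value is calculated as" one minus half of p. Two places in the same section bear on which estimate is meant:

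- The t-test code is introduced as the "syntax that will be used to obtain the two-sided confidence intervals around the" Δ_T estimates. There the estimate is the mean.
- The bootstrap code gives intervals around the Δ_T "medians (in case Wilcoxon test is used) by using Bootstrapping is". There the quantity is the median.

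Neither place settles the tail rule. On timepoints the section says: "The analysis will be performed at T0, T10, T20, and T30".

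**The concern.** A signed-rank test discards zero differences and ranks the absolute size of the rest. Its direction is therefore the sign of S, the positive rank sum minus its null expectation. The SAP's rule never mentions S and relies on a separate location estimate instead. If that estimate is the sample median, the two can disagree. The likeliest way is a median of exactly 0 caused by tied zeros, which the rule sends to the 1 − p/2 branch even when the non-zero differences clearly favour the lidocaine product.

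Zeros can arise in three ways: the VAS has a floor at 0 mm (SAP 8.1.1), missing T0 differences are imputed as 0 mm (SAP 10.4.6.3), and the same code is run up to 30 minutes after injection, when both hands may score near 0. The documents give no VAS levels, so the last is a supposition. SAP 10.4.6.3 expects very few imputed zeros at T0.

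Two programmers could follow the SAP faithfully and report opposite tails. A Wilcoxon p near 1 could then stand beside a significant t-test. Protocol 6.4.3.1 says non-parametric methods will be used when normality fails, so a reader of the protocol may give this p-value more weight than the SAP does.

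**Working it through.** **Inputs.** From SAP 7: mean difference −10 mm, SD 25 mm, 80 evaluable and about 90 randomized subjects. From SAP 10.1.5: one-sided α = 0.025. The share of zeros, the VAS levels and the between-hand correlation are assumptions.

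**The plan's own figure.** The noncentral t power for a one-sample test with −10/25 at one-sided 0.025 is 0.8973 at n = 67 and 0.9016 at n = 68. The stated 68 is reproduced, and the sample size is not in question.

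**One worked data set, n = 90:** 40 differences of −10 mm, 30 of 0, 20 of +3 mm.

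- Median: the 45th and 46th ordered values are both 0, so the median is 0. Mean: (−400 + 60)/90 = −3.8 mm.
- Dropping zeros leaves m = 60. The 20 values of size 3 share rank 10.5; the 40 of size 10 share rank 40.5.
- S = (20 × 10.5 − 40 × 40.5)/2 = (210 − 1620)/2 = −705.
- Tie-corrected variance: V = m(m+1)(2m+1)/24 − Σt(t+1)(t−1)/48 = 18,452.5 − (63,960 + 7,980)/48 = 16,953.75.
- T = S·√[(m−1)/(mV − S²)] = −705·√(59/520,200) = −7.51 on 59 df; two-sided p = 3.7e-10.
- Tail by the sign of S, or by the mean: about 2e-10. Tail by the median: 1 − p/2, about 1.

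The sample median here is 0, so the example shows the wrong tail of the signed-rank test. It does not show that the population median is negative.

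**Simulation A: zeros added.** Differences N(−10, 25) rounded to 1 mm, with a given share set to 0; 10,000 trials per cell. The table counts trials with one-sided p < 0.025 by the sign of S, and how many of these the median reading reports as ≥ 0.025.

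| Added zeros | Population share below 0 | n = 80 | n = 90 |
|---|---|---|---|
| 0% | 64.8% | 0/9344 (0%) | 0/9533 (0%) |
| 5% | 61.6% | 17/9202 (0.2%) | 14/9495 (0.15%) |
| 10% | 58.3% | 161/9046 (1.8%) | 165/9397 (1.8%) |
| 15% | 55.1% | 799/8900 (9.0%) | 813/9206 (8.8%) |
| 20% | 51.8% | 2065/8633 (24%) | 2362/9054 (26%) |

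The share below 0 reaches 50% at 1 − 0.5/0.648 = 23% added zeros, so the table stops before that. In every row the population median is negative and the SAP's median alternative is true.

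**Simulation B: zeros from the VAS floor.** Latent normal score per hand, SD 25, correlation 0.5 (difference SD 25), lidocaine hand 10 mm lower, rounded and cut to 0–100; 10,000 trials per cell. Latent Restylane Vital means were 50, 30, 20, 15 and 12 mm.

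| Observed Restylane Vital mean | Exact zeros | Share below 0 | n = 80 | n = 90 |
|---|---|---|---|---|
| 50 mm | 2% | 64% | 0/9280 (0%) | 0/9525 (0%) |
| 31 mm | 7.5% | 61% | 18/9085 (0.2%) | 22/9418 (0.2%) |
| 23 mm | 15% | 57% | 338/8939 (3.8%) | 371/9226 (4.0%) |
| 19 mm | 20% | 53% | 1418/8689 (16%) | 1404/9063 (15%) |
| 17 mm | 24% | 51% | 2547/8568 (30%) | 2829/8984 (31%) |

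**Mean reading and the opposite error.** With the tail set by the mean, none of the 91,810 + 90,777 = 182,587 significant trials flipped. False support under the median reading occurred in 0 of 200,000 trials.

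**Is naming the mean enough?** Not in every data set. Take n = 80 with 55 negatives of −(1 + 0.3k) mm for k = 1 to 55, 5 zeros and 20 values of +90. The mean is +16, S = −115, and the mean rule gives 0.73 where S gives 0.27. The median can also have the opposite sign to S without being 0: 46 values of −2 and 44 of +20 give median −2 and S = (44 × 68.5 − 46 × 23.5)/2 = +966.5. Both sets were constructed for the purpose. In the second the mean is +8.8 mm and the t-test gives no support either.

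**The case against.** The case against has five parts.

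- **Wording.** SAP 12.5 calls the mean an estimate and uses a different word, medians, when it means the median. On that reading no simulated trial is affected. This stands as a plausible reading, but it is not fixed anywhere, and SAP 10.4.3 points the other way.
- **Hypothesis.** A sample median of 0 lies inside the null hypothesis of SAP 10.4.3, so a large p may seem fitting. But 1 − p/2 is then not the p-value of the signed-rank test in the stated direction, and in every simulated cell the population median is negative.
- **Reach.** The primary decision is the t-test ("If the one-sided p-value of the test is <0.025 the pain at the end of injection will be considered statistically significantly lower after treatment"). The Wilcoxon test is conditional, and SAP 10.4.6.6 makes non-primary p-values descriptive. The simulated error was only ever conservative. All of this stands.
- **Visibility.** In re-runs with 3,000 trials per cell at n = 80, about 94–98% of flipped trials also had a significant t-test, wherever flips were at all common. SAP 10.4.1.1 tabulates means and medians, and "subjects that have a within-subject difference of less than 0 mm on the VAS will be summarized at each post-treatment timepoint". The conflict would probably be seen, though it would then have to be explained after unblinding.
- **Inputs.** No document supports 20–24% exact zeros, and the T10 to T30 case borrows the T0 planning effect. The simulations also ignore the normality trigger. With Shapiro–Wilk p < 0.05 as a stand-in (an assumption), the affected share falls from 2.2% to 0.8% at 10% zeros, from 8.6% to 5.6% at 15%, and from 25% to 20% at 20%. The larger percentages are therefore hypothetical.

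Part of the SAP text on the other endpoints is redacted, so a definition could stand there. The rule in SAP 12.5 itself is fully visible and contains none.

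**Conclusion.** The concern holds as a minor point. The stated rule does not determine the tail, and under the median reading it returns the wrong one whenever S is negative and the median is exactly 0. How often that happens depends on the share of exact zeros, which the documents do not give: never in the simulated trials at the planning values, about 0.2% of significant trials at 5% added zeros, and 24–26% at 20%. Under the mean reading the simulated rate is zero. The SAP's primary conclusion does not depend on it.

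**What to change.** In SAP 12.5, replace the sign of the Δ_T estimate with the sign of the signed-rank statistic S from the same TestsForLocation output: one-sided p = p/2 if S < 0, otherwise 1 − p/2. If S = 0, both branches give 0.5. This is better than naming the mean or the median, because it agrees with the test in every data set.

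The cost is two lines of SAP text. The statistic is in a table the code already saves, and the change affects neither the data nor the subjects.
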